To determine the feasibility of initiating a continuous glucose monitoring in patients with diabetes at hospital discharge. We hypothesize that starting and continuing to use a CGM at this critical time is feasible. Feasibility is defined as at least 20% of patients with diabetes referred for diabetes education meet inclusion criteria to participate and 75% agree to

participate. From those who participate, at least 50% continue using the CGM at 3 months.

B2 Secondary Aims

1. To characterize the barriers to continuing CGM use after discharge. We will systematically characterize the reasons for discontinuations (issues with wearing device, use, costs, getting refills, etc.)
2. To assess the effect of CGM initiation at hospital discharge on diabetes outcomes: Time in range, health utilization (clinic visits, ED visits, hospitalization), self-efficacy.

C Study Design

C1 Overview or Design Summary

This study will be an interventional, single-arm, open-label, prospective design.

C2 Subject Selection and Withdrawal

One hundred eligible adult patients will be recruited to the study.

2.a Inclusion Criteria

1. 18 years of age or older
2. Have diabetes (type 1 diabetes mellitus, type 2 diabetes mellitus, cystic fibrosis related diabetes mellitus)
3. Hemoglobin A1c greater than or equal to 8.0% or history of hypoglycemia unawareness
4. Able and willing to sign informed consent form
5. Have a valid telephone number
6. Willing to purchase FreeStyle Libre 2 CGM sensors out of pocket after discharge from hospital

2.b Exclusion Criteria

1. Unable to sign informed consent form
2. Have altered mental status
3. Unable to manage diabetes independently at home
4. Have utilized CGM in the past
5. Pregnancy
6. New steroid-induced hyperglycemia
7. Unwilling to participate in the study
8. Have kidney disease requiring hemodialysis
9. Taking high doses of vitamin C daily (greater than 500 mg every day)

2.c Subject Recruitment Plans and Consent Process

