The study team will identify potential participants from patients referred to the diabetes service or diabetes education service. Once a participant is identified, one of the study team members will approach the patient in their private hospital room, review the study and provide them with a written informed consent form to review. The study team will follow up 1-2 days later or prior to discharge to determine if the patient is interested in participating. If the patient is interested, the study team will review the informed consent form with them, answer all study related questions and obtain written informed consent. If a patient is not interested in the study, the study team will not coerce them into participating; participation is completely voluntary.

2.d. Risks and Benefits

Participants may or may not benefit from participating in the study. Benefits of participating in the study may include the following:

1. Improved understanding of diabetes
2. Improved ability to manage diabetes
3. Discover glucose patterns previously unaware of.

Potential risks of participating in the study include the following:

1. Improperly treated diabetes risks may include: hypoglycemia, hyperglycemia, or ketoacidosis.
2. CGM sensor insertion risks may include: feeling like insulin injection; tenderness at the sensor site.
3. Pain, redness, swelling, minor infection and minor bleeding at the sensor insertion site.
4. Redness may occur where the device adhesive pads are placed.
5. Allergic reaction to one of more parts of the sensor.
6. Skin may blister or peal at the site of the sensor.
7. Sensor or insertion needle may break.
8. Fingerstick testing risks may include: finger feel sore, tender or may bleed.
9. Questionnaire risks may include: some questions may cause the participant to feel uncomfortable.

2.e. Early Withdrawal of Subjects

Participants may be withdrawn if certain situations arise:

1. Participant does not follow study instructions
2. Change in participant's medical condition (i.e., pregnancy, worsening clinical condition)
3. The study team or government agencies stop the study
4. In the opinion of the study team, there is no value in participant continuing the study.

5. If new information becomes available or harmful unexpected reactions are experienced by participants in the study.

C3 Study Device

3.a Description

FreeStyle Libre 2 Continuous Glucose Monitoring System manufactured by Abbott

D Study Procedures

D1 Screening for Eligibility

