The study team will identify potential participants from patients referred to the diabetes service or diabetes education service. Once a potential patient has been identified, one of the study team members will review the inclusion/exclusion criteria to determine if the patient is eligible to participate.

D2 Schedule of Measurements

VISIT/PHONE CALL (estimated time window)	WHAT WILL HAPPEN?
Screening Visit (~45 minutes)	Review consent form and obtain consent Complete questionnaire, obtain diabetes history
Day of Discharge (~1 hour)	Complete FreeStyle Libre 2 CGM education Attach FreeStyle Libre 2 CGM sensor to your arm
Within 1-3 weeks from discharge Phone Call (~30 minutes)	Questions regarding use of FreeStyle Libre 2 CGM Current diabetes regimen Adverse Events Reminder to take FreeStyle Libre 2 CGM sensor prescription to pharmacy to be filled
1 & 3 Month Phone Call (~45 minutes) [+/- 5 days]	Questions regarding use of FreeStyle Libre 2 CGM Current diabetes regimen Complete questionnaire Adverse Events
6 Month Phone Call (~15 minutes) [+/- 10 days]	Questions regarding use of FreeStyle Libre 2 CGM Barriers to FreeStyle Libre 2 CGM use

D3 Visit 1a: During Hospital Stay

Study team member will meet with participant, review informed consent form and obtain written consent. Study team member will obtain the following information from patient or medical record after consent is obtained:

1. Most recent A1c

- 2. Height/Weight; calculate body mass index (BMI)
- 3. Year of diagnosis with diabetes
- 4. Type of diabetes
- 5. Has patient been admitted to the hospital or emergency department in the past 3 months for a diabetes related problem
- 6. Home diabetes regimen
- 7. Hospital diabetes regimen
- 8. Hospital discharge treatment regimen
- 9. Participant's reason/goal for using FreeStyle Libre 2 CGM
- 10. Does participant have frequent hypoglycemia or hypoglycemia unawareness
- 11. Complete "Diabetes Self-Management Questionnaire"

D4 Visit 1b: Day of Hospital Discharge:

On the day of participant's discharge from the hospital, one of the diabetes educators will complete the following with the participant:

- 1. Teach participant how to set up the FreeStyle Libre 2 CGM
- 2. Teach participant how to attach the FreeStyle Libre 2 CGM sensor to the upper arm
- 3. Teach participant how to measure blood glucose with FreeStyle Libre 2 CGM reader or personal smart phone
- 4. Assist participant download the free FreeStyle Libre 2 app from the app store on smart phone

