- 5. Teach participant how to trouble shoot the FreeStyle Libre 2 CGM system
- 6. Provide participant with a handout for FreeStyle Libre 2 CGM system

The study physicians or nurse practitioners will provide the participant with a written prescription for three months of the FreeStyle Libre 2 CGM sensors to be filled by participant at their local pharmacy.

D5 Follow Up Telephone Calls

Within 1-3 Weeks after Discharge:

The study team will contact the participant by telephone to obtain the following information:

- 1. Is the participant still utilizing the FreeStyle Libre 2 CGM? If not, why was it stopped?
- 2. What barriers (such as discomfort, behavior modifications, lifestyle changes, diet changes) did the participant have with the FreeStyle Libre 2 CGM to limit use?
- 3. How satisfied with the FreeStyle Libre 2 CGM is the participant?
- 4. Has the participant been admitted to the hospital or been in the emergency department for a diabetes related problem since discharge?
- 5. Has the participant seen their outpatient diabetes provider since discharge?
- 6. What is the participant's current diabetes treatment regimen?

7. The study team will contact the participant to remind them to fill the prescription for a new FreeStyle Libre 2 CGM sensor with local pharmacy.

One Month after Discharge (+/- 5 days):

The study team will contact the participant by telephone to obtain the following information:

1. Is the participant still utilizing the FreeStyle Libre 2 CGM? If not, why was it stopped?
2. What is the average blood glucose for the past 30 days?
3. What barriers (such as discomfort, behavior modifications, lifestyle changes, diet changes) did the participant have with the FreeStyle Libre 2 CGM to limit use?
4. How satisfied with the FreeStyle Libre 2 CGM is the participant?
5. Has the participant been admitted to the hospital or been in the emergency department for a diabetes related problem since discharge?
6. Has the participant seen their outpatient diabetes provider since discharge?
7. What is the participant's current diabetes treatment regimen?
8. Administer the Diabetes Self-Management Questionnaire

Three Months after Discharge (+/- 5 days):

The study team will contact the participant by telephone to obtain the following information:

1. Is the participant still utilizing the FreeStyle Libre 2 CGM? If not, why was it stopped?
2. What is the average blood glucose for the past 30 days?

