3. What barriers (such as discomfort, behavior modifications, lifestyle changes, diet changes) did the participant have with the FreeStyle Libre 2 CGM to limit use?
4. How satisfied with the FreeStyle Libre 2 CGM is the participant?
5. Has the participant been admitted to the hospital or been in the emergency department for a diabetes related problem since discharge?
6. Has the participant seen their outpatient diabetes provider since discharge?
7. What is the participant's current diabetes treatment regimen?
8. Administer the Diabetes Self-Management Questionnaire

Six Months after Discharge (+/- 10 days):

The study team will contact the participant by telephone to obtain the following information:

1. Is the participant still utilizing the FreeStyle Libre 2 CGM? If not, why was it stopped?

2. What barriers (such as discomfort, behavior modifications, lifestyle changes, diet changes) did the participant have with the FreeStyle Libre 2 CGM to limit use?

E Safety Monitoring

E1 Safety and Compliance Monitoring

The study team will meet every other week to review the status of the study, progress of recruitment, and adverse events. The study team will communicate directly with one another in between scheduled study team meetings if an unexpected adverse event occurs.

E2 Medical Monitoring

The study team will monitor patients throughout their participation in the study. Any adverse event or unexpected adverse event will be brought to the principal investigator within 24 hours of study team notification of event.

F Statistical Plan

F1 Sample Size Determination and Power

One hundred patients will be recruited for the study with the anticipation that 50% will agree to participate in the study.

F2 Statistical Methods

Statistical methods will include descriptive statistics (means, SD, median, IQR) and pre-test/post-test ANOVA for the questionnaire.

G References

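### Secondary aim 2 promises an effect of CGM initiation that one arm without a comparator cannot identify, and for glucose the plan collects no matching pre-CGM value.

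*Combined protocol and SAP*

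**What the plan says.** B2, aim 2, reads: "To assess the effect of CGM initiation at hospital discharge on diabetes outcomes". It names three: time in range, use of health care (clinic, emergency and hospital) and self-efficacy. C1 describes the design: "This study will be an interventional, single-arm, open-label, prospective design". No concurrent control, historical series or external benchmark appears anywhere.

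Patients are found during a hospital stay. C2 2.c and D1 state: "The study team will identify potential participants from patients referred to the diabetes service or diabetes education service". The glycaemic entry criterion (2.a, item 3) has two alternative routes: "Hemoglobin A1c greater than or equal to 8.0% or history of hypoglycemia unawareness".

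Before the sensor is attached, D3 records "Most recent A1c", diabetes-related hospital or emergency use over the preceding 3 months, the home, hospital and discharge regimens, and the Diabetes Self-Management Questionnaire. At 1 and 3 months, D5 repeats the questionnaire and asks: "What is the average blood glucose for the past 30 days". The calls at 1-3 weeks, 1 month and 3 months ask about hospital or emergency use, and visits to the outpatient diabetes provider, since discharge.

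F2 plans descriptive statistics and "pre-test/post-test ANOVA for the questionnaire". It names no other test and says nothing about how a change is to be interpreted.

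**The concern.** An effect is a contrast between what happened with CGM and what would have happened without it. This plan observes only the first. Several other things change at the same moment as CGM starts: the patient leaves hospital, has been referred to a diabetes or education service, and may go home on a different regimen. Participants must also be willing to buy sensors themselves, and the outcomes are reported by telephone in an open-label study. Any of these could move the outcomes without a contribution from the device.

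At stake is the conclusion drawn for aim 2. A significant questionnaire change, reported under an aim worded as an effect, invites the reader to credit CGM with all of it. The primary feasibility aim is not affected.

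**Working it through.** F1 gives no alpha, power, effect size, standard deviation or precision target, so the plan has no figure for aim 2 to reproduce. The check sets each outcome's baseline beside its follow-up.

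| Aim 2 outcome | Before CGM (D3) | After discharge (D5) | Planned analysis (F2) | What can be computed |
|---|---|---|---|---|
| Self-efficacy | Questionnaire, in hospital | Questionnaire at 1 and 3 months | Pre/post ANOVA | Within-person change, uncontrolled |
| Hospital/ED use | 3-month look-back | Since discharge, three calls | Descriptive | A before-after contrast whose baseline is tied to an admission |
| Clinic visits | None listed | Diabetes provider seen since discharge | Descriptive | Follow-up proportion only |
| Time in range | None listed | In no call list | Descriptive | Nothing, as the lists stand |
| Average glucose (not named in aim 2) | None listed; A1c recorded once | 30-day average at 1 and 3 months | Descriptive | Change from 1 to 3 months only, both on CGM |

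**Questionnaire.** This is the only outcome with both a matching baseline and a planned test. The documents give no score distribution, so the non-device part of any change cannot be estimated. How readily the test would pick up such a shift can be shown. Treat the ANOVA as a paired contrast and assume two-sided alpha 0.05. The standardized mean change that gives significance with 80% probability is (1.96 + 0.84)/√n:

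- n = 100: 2.80/10 = 0.28
- n = 50: 2.80/7.07 = 0.40
- n = 25: 2.80/5 = 0.56

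C2 says 100 patients will be recruited, whereas F1 expects 50% to agree, so 100 and 50 are both possible readings before any loss to follow-up; 25 is half of the smaller figure. The units are standard deviations of within-person change. The test responds in the same way whether the shift comes from CGM, education, regimen change or recovery.

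**Hospital and emergency use.** The baseline question is put to people who are in hospital when they answer. D3 does not say whether the current admission counts. If it does, and was diabetes-related, the baseline is positive by design and a later fall is expected without CGM. If it does not count, enrolment still happens at a time of hospital use.

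**Glucose.** Baseline A1c is not repeated at any call and is on a different scale from a 30-day average. The first average is asked for at 1 month, after CGM has started. If only the 50% required by B1 are still using CGM at 3 months, 3-month sensor glucose comes from about 50 of 100 or 25 of 50 participants.

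**A1c, as illustration only.** Suppose the referral pool has mean A1c 8.5%, SD 2.0 and repeat correlation r (all assumed), and everyone enters at 8.0% or above. With c = (8.0 − 8.5)/2.0 = −0.25, the selected mean is 8.5 + 2.0 × φ(c)/(1 − Φ(c)) = 8.5 + 1.29 = 9.79%. The expected fall on a repeat test with no treatment effect is (1 − r) × 1.29, which is 0.39, 0.26 and 0.13 points for r = 0.7, 0.8 and 0.9. Over pool means of 7.5-8.5%, SDs of 1.5-2.0 and r of 0.6-0.9, the range is 0.09 to 0.77 points. The trial takes no repeat A1c, so this does not size the bias of any planned outcome.

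**The case against.** The best defence is that this is a feasibility study. Its stated goal and its only hypothesis concern feasibility, the single arm is declared openly, aim 2 is secondary with no alpha or threshold, and F2 is descriptive for everything except the questionnaire. On this view the word effect is merely loose. Regimens are also recorded at baseline and at the first three calls, so changes in treatment can at least be described.

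Much of this stands. F2 names a method and does not itself attribute change to the device. But B2 asks for an effect, no passage limits how a change may be read, and no planned analysis uses the regimen data.

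Three stronger readings are tempting, and the documents do not support them:

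- *No glucose measure exists before CGM.* A1c is recorded in D3. What is missing is a baseline on the scale of the follow-up measures, or a repeat A1c.
- *Natural recovery will be reported as a glucose benefit.* No pre-to-post glucose change can be computed and no glucose test is planned. The glucose problem is that the aim cannot be answered, rather than that it will be answered with bias.
- *Participants are selected at a glycaemic peak, so regression to the mean gives the size of the error.* An A1c of at least 8.0% is one of two entry routes and no split is given; those entering on hypoglycemia unawareness need not have high glucose. Nobody is selected on the questionnaire score, so the A1c figures do not carry over to it. Nor do the documents say that the index admission is for diabetes.

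**Conclusion.** The point holds as a mismatch between aim and design. One arm without a comparator cannot deliver the effect that aim 2 promises for any of its three outcomes, and the reason differs by outcome. For self-efficacy, a real within-person change can be estimated but not attributed to CGM. For hospital and emergency use, the baseline is tied to an admission; for clinic visits there is none. For time in range, the plan lists neither a baseline nor a follow-up collection.

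The direction of any misreading is likely to favour CGM, since education, regimen optimization and recovery would be expected to help. That is a judgement; the documents do not establish it, and its size cannot be derived from them. The 0.28 and 0.40 standard-deviation figures for 100 and 50 pairs rest on an assumed two-sided 5% level and a paired approximation. They describe the test's sensitivity to a shift from any cause and do not estimate bias. The A1c figures are illustration only.

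The consequence is confined to a secondary aim, but it changes what the study may conclude there, so it should be corrected.

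**What to change.** - **B2, aim 2:** restate as *to describe diabetes outcomes and within-person change after CGM initiation*.
- **F2, interpretation:** state that change will not be attributed to CGM.
- **Questionnaire:** report mean change from the in-hospital baseline to 3 months with a 95% confidence interval, labelled as uncontrolled change. The approximate half-width is 1.96/√n standard deviations of change: 0.20 for 100 pairs and 0.28 for 50.
- **Utilization:** report hospital, emergency and clinic use descriptively, without a before-after claim.
- **Glucose:** report the 1- and 3-month values descriptively. Label any paired change as coming from people with data at both calls, in practice mainly continuing users. Either state how time in range is obtained, noting that even the first sensor period is already on CGM, or do not name it as an outcome.

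The cost is a weaker secondary claim. The rewording needs no new data and no change in sample size; keeping time in range would need a stated source for it.

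A concurrent control is the alternative if an effect is wanted, but it is not cheap. For two equal arms at two-sided 0.05 and 80% power, n per arm = 2 × (1.96 + 0.84)²/d², which is 175, 99 and 63 for assumed standardized differences d of 0.3, 0.4 and 0.5. Splitting 100 patients into 50 per arm gives power of about 32%, 52% and 70%.

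### B1's 75% agreement criterion has no stated denominator, inclusion 4 and exclusion 7 allow a refuser to be counted as ineligible, and F1 anticipates 50% agreement against B1's 75%

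*Combined protocol and SAP*

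**What the plan says.** B1 defines feasibility by three proportions. The first two come in one sentence: at least 20% of "patients with diabetes referred for diabetes education meet inclusion criteria to participate and 75% agree to" participate. The third is that at least half of participants are still using the monitor at 3 months. The first and third proportions name their denominators; the 75% does not.

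Willingness appears in both eligibility lists. Inclusion 4 is "Able and willing to sign informed consent form" and exclusion 7 is "Unwilling to participate in the study". Under D1 the team must "review the inclusion/exclusion criteria to determine if the patient is eligible to participate". The Screening Visit row of D2 includes "Review consent form and obtain consent".

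Section 2.c describes a sequence of identification, approach and then a decision: "The study team will follow up 1-2 days later or prior to discharge to determine if the patient is interested in participating". It says decliners will not be pressed, but not how they are counted. F2 does not define the feasibility proportions.

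On numbers, C2 says "One hundred eligible adult patients will be recruited to the study", and F1 says "One hundred patients will be recruited for the study with the anticipation that 50% will agree to participate in the study".

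B1 counts referrals for diabetes education, whereas 2.c and D1 draw patients from either the diabetes service or the education service.

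**The concern.** Willingness items are common in enrolment lists and usually harmless. They matter here because eligibility and agreement are themselves primary outcomes. If willingness is part of eligibility, someone who refuses never enters the denominator of the agreement rate. The 75% criterion is then met almost by construction, and the 20% criterion measures eligibility multiplied by acceptance.

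What is at stake is the answer on two of the three primary criteria. In part of the plausible range the verdict on the two together changes with how refusals are logged. In another part both counts fail, but one blames too few eligible patients and the other too few agreeing, which would lead to different next steps.

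F1 raises a separate problem: its anticipated agreement rate is below the rate that B1 requires, and it leaves the number of participants unclear.

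**Working it through.** **The plan's own figure.** N = 100 cannot be reproduced. The protocol gives no precision target, error rate, power or null and alternative rates.

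**Inputs.** From B1: thresholds of 20%, 75% and 50%. From F1: 100 patients and 50% agreement. Assumed: c, the share of referrals meeting every criterion apart from willingness to consent or take part, which the documents do not give. Acceptance among those patients is a; F1's 50% is used as one value.

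**Two ways to count.**
- Literal (refuser is ineligible): eligibility = c × a; agreement = about 100%. Both criteria pass if c × a ≥ 20%.
- Separated (refuser is eligible but declined): eligibility = c; agreement = a. Both pass if c ≥ 20% and a ≥ 75%.

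**Where the joint verdict differs.**
- Literal passes and separated fails: a < 75% and c ≥ 20%/a. This means c ≥ 0.20/0.50 = 40% at a = 50%, 0.20/0.60 = 33.3% at 60%, and 0.20/0.70 = 28.6% at 70%.
- Literal fails and separated passes: a ≥ 75% and 20% ≤ c < 20%/a. The upper limit is 0.20/0.75 = 26.7% at a = 75%, 0.20/0.80 = 25% at 80%, and 0.20/0.90 = 22.2% at 90%.

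| c (assumed) | a | Literal: eligibility, agreement | Separated: eligibility, agreement |
|---|---|---|---|
| 40% | 50% | 20%, about 100%: pass | 40%, 50%: fail |
| 25% | 75% | 18.75%, about 100%: fail | 25%, 75%: pass |
| 30% | 50% | 15%, about 100%: fail | 30%, 50%: fail |
| 30% | 75% | 22.5%, about 100%: pass | 30%, 75%: pass |

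In the third row both counts fail, but the literal count points to eligibility and the separated count to agreement. At F1's 50% both counts fail for every c below 40%. At a = 80% both fail for c below 20% and both pass for c of 25% or more.

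**Which list item carries the point.** B1 refers to inclusion criteria, so inclusion 4 alone is enough. Exclusion 7 affects the 20% only if B1's phrase is read as full eligibility, as D1 determines it.

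**F1 against B1.** 75 − 50 = 25 percentage points short, if both figures refer to eligible patients approached.

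**Meaning of 100.** If 100 are approached and 50% agree, there are 100 × 0.50 = 50 participants. If 100 are enrolled at 50% acceptance, 100/0.50 = 200 must be approached. An observed 50% on the 3-month criterion then has a Wilson 95% confidence interval of 36.6% to 63.4% (25/50) or 40.4% to 59.6% (50/100).

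**The case against.** The strongest reply is that no sensible team would count this way. B1 lists eligibility, agreement and continuation as successive steps; 2.c asks about interest after the patient has been identified and approached; and F1 allows for people who do not agree. The natural denominator for the 75% is patients who meet the criteria, with refusers among them. D2's Screening Visit row is weak evidence the other way, since it is written for participants and D3 calls the consent meeting Visit 1a. All of this stands. A reader might infer that the trial will in fact log refusers as ineligible, or that its agreement rate is bound to be meaningless; the documents do not show that. What remains is that the written eligibility rules give the wrong proportion and nothing overrides them.

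A reader might also infer that the feasibility verdict always depends on the count. It does not: it changes only in the ranges shown, c is assumed, and the comparison covers two of three criteria. If 3-month continuation is below 50%, overall feasibility fails under either count.

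Nor do the documents establish that the plan expects to fail. F1 states no denominator for its 50%, which may be a cautious recruitment assumption or a slip for the 50% continuation criterion. In either case F1 needs correcting or explaining.

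Finally, one might want patients who will not pay for sensors (inclusion 6) moved into the 75% denominator. Inclusion 6 does not cause the circularity, and moving it would turn the measure into agreement including refusal to pay, against a threshold not set for that. Separate reporting makes cost visible without this change.

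**Conclusion.** The point holds. As written, the eligibility rules make willingness part of the 20% criterion and leave the 75% criterion without an independent denominator. The intended count is probably the separated one, but the protocol does not say so. The joint verdict on the two criteria differs only if a < 75% with c ≥ 20%/a, or a ≥ 75% with 20% ≤ c < 20%/a. Outside those ranges the effect is confined to the reported proportions and, in some cases, the apparent reason for failure. These ranges follow from B1's thresholds; whether the trial falls inside them depends on c, which the documents do not give.

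F1's 50% and B1's 75% are inconsistent if both describe eligible patients approached, and C2 with F1 leaves the number of participants at 50 or 100. This second finding does not depend on the first.

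Both should be settled before refusals are counted, because a refusal not recorded as such at the time may not be recoverable later.

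**What to change.** Leave the enrolment criteria as they are and make these changes.

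1. Add a counting rule to B1. For the feasibility proportions, a patient is eligible if all criteria are met except the willingness part of inclusion 4 and exclusion 7. The denominator of the 75% is all such eligible patients approached.
2. Record each refuser prospectively as eligible but declined, with the reason.
3. Keep inclusion 6 within eligibility, but count and report patients who fail it as a separate category. The background names cost as a significant barrier, and B2 aim 1 captures it only as a reason for stopping after enrolment.
4. Reconcile F1's 50% with B1's 75%, or state what the 50% refers to.
5. State in C2 and F1 whether 100 is the number approached or enrolled.
6. Use one referral pool, either the education service alone or both services, for the numerator and denominator of the 20%.

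The cost is a few sentences and a short record of decliners, which the protocol does not now describe. Visits and procedures do not change. If 100 means enrolled, about 200 eligible patients must be approached at 50% acceptance. The reported agreement rate will be lower than under the literal count, and at 50% the 75% criterion would not be met.

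### B1's 20% eligibility and 75% agreement criteria may rest on a selected group, because 2.c and D1 do not require every referral to be reviewed or every eligible patient to be approached

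*Combined protocol and SAP*

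**What the plan says.** B1 (Primary Aim) defines feasibility by three proportions. The first is that "at least 20% of patients with diabetes referred for diabetes education meet inclusion criteria to participate". The second follows in the same sentence: "meet inclusion criteria to participate and 75% agree to" take part. Its denominator is not written out; the natural reading is patients who meet the criteria. The third is "From those who participate, at least 50% continue using the CGM at 3 months", which is not at issue here.

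Recruitment is described in 2.c and again in D1. Both begin: "The study team will identify potential participants from patients referred to the diabetes service or diabetes education service". D1 continues: "Once a potential patient has been identified, one of the study team members will review the inclusion/exclusion criteria". 2.c continues: "Once a participant is identified, one of the study team members will approach the patient in their private hospital room". Neither section says how a potential participant is recognised, whether all or consecutive referrals are considered, or whether a screening log is kept.

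The eligibility lists in 2.a and 2.b include willingness. Inclusion 4 is "Able and willing to sign informed consent form", inclusion 6 is "Willing to purchase FreeStyle Libre 2 CGM sensors out of pocket after discharge from hospital", and exclusion 7 removes patients who do not want to take part.

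F2 lists summary statistics and a before-and-after ANOVA for the questionnaire. It gives no denominator or analysis for the feasibility proportions.

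**The concern.** In most trials, loose wording about how candidates are found does no harm, because the screening yield is not an outcome. Here it supplies two of the three feasibility criteria. To estimate eligibility among referrals, the team needs an eligibility status for every referral or for a defined sample of them. The order in D1, identification and then review, leaves that status unknown for any referral not identified.

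The effect depends on how such patients are handled. Leaving likely ineligible patients out of the count inflates eligibility. Counting them without review understates it, because any eligible patients among them can never reach the numerator. Naming the right denominator is therefore not enough; the plan also needs a rule for who is reviewed. Agreement is distorted if the patients approached differ in willingness from the eligible patients not approached. Willingness generally cannot be recovered afterwards from records.

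**Working it through.** **The plan's own figure.** F1 gives 100 patients and an anticipated 50% agreement. No significance level, power, null rate or precision target is stated, so the 100 cannot be reproduced. It is used below only for workload.

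**Inputs.** From B1: thresholds of 20% and 75%. Assumed, because the documents give no figures: the true rates, and the share f of referrals set aside without review (range 20% to 50%).

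**Eligibility, patients set aside not counted.** If all of them are ineligible, observed = true / (1 − f).

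**Eligibility, patients set aside counted but not reviewed.** If their eligibility matches the rest, observed = true × (1 − f).

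| True rate and handling | f = 20% | f = 30% | f = 40% | f = 50% |
|---|---|---|---|---|
| 12%, not counted | 15% | 17.1% | 20% | 24% |
| 15%, not counted | 18.75% | 21.4% | 25% | 30% |
| 25%, counted | 20% | 17.5% | 15% | 12.5% |
| 30%, counted | 24% | 21% | 18% | 15% |

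At f = 20% no row changes its verdict against the 20% threshold. At 30% the second and third rows do, and at 40% all four do. The two ways of handling the patients push in opposite directions.

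**Agreement.** Let a be true agreement and g the share of would-be decliners who are never counted, with all would-be agreers counted. Then observed = a / [a + (1 − a)(1 − g)].

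- a = 60%, g = 25%: 0.60 / (0.60 + 0.40 × 0.75) = 66.7%.
- a = 60%, g = 50%: 0.60 / (0.60 + 0.40 × 0.50) = 75%.
- a = 50%, g = 50%: 0.50 / (0.50 + 0.50 × 0.50) = 66.7%.

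If selection is unrelated to willingness, agreers and decliners are lost in the same proportion and the rate does not move.

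**Willingness inside eligibility.** Take 1,000 referrals at B1's own rates. If eligibility excludes willingness, 0.20 × 1,000 = 200 are eligible and 0.75 × 200 = 150 agree. Read literally, inclusion 4 and exclusion 7 make the 50 decliners ineligible. Eligibility becomes 150 / 1,000 = 15% and agreement 150 / 150 = 100%. The same patients then fail the first criterion and pass the second automatically, however complete the log.

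**Workload if every referral is reviewed, at 20% eligibility.**

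- 100 enrolled at 75% agreement: 100 / (0.20 × 0.75) = about 667 referrals.
- 100 enrolled at 50% agreement: 100 / (0.20 × 0.50) = 1,000.
- 100 approached: 100 / 0.20 = 500.

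**The case against.** The strongest reply is that the documents never say any referral goes unreviewed. Identifying candidates from referrals can mean that the referral itself identifies them. B1 names education referrals as the denominator, so counting only reviewed patients would contradict the plan. 2.c, read plainly, approaches everyone identified. Nothing suggests that staff favour patients who look willing, and every illustration rests on assumed shares.

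Much of this stands. A reader might infer that the team picks patients at its own discretion in place of screening all referrals, and that both rates are in fact computed on a selected group. The documents do not support that: no section describes such a practice, and the wording is compatible with complete screening. The numerical examples show what could happen, not what will.

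The reply does not close the gap. B1 fixes the denominator of the first criterion but does not make anyone establish eligibility for everyone in it. If referrals go unreviewed, adhering to B1's denominator turns possible inflation into understatement. No other section, including F2, supplies the missing rule.

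**Conclusion.** The plan does not secure the data needed for two of its three feasibility criteria. It leaves open whether all education referrals are reviewed and whether all eligible patients are approached, so a pass or a fail on either rate would be hard to interpret.

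The size and direction of any bias are unknown. Under the assumptions shown, setting aside 20% of referrals changes none of the four eligibility verdicts, while 30% to 40% can turn a fail into a pass or the reverse. Bias in agreement requires selection related to willingness, which is possible but not documented. The willingness items in the eligibility lists are a firmer problem, because they rest on the text alone and must be dealt with for any log to be useful.

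This should be corrected before recruitment. It does not show that the trial will give a wrong answer.

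**What to change.** 1. In 2.c and D1, state that every consecutive patient with diabetes referred for education during recruitment is reviewed and entered in a screening log. If staffing does not allow this, fix screening days in advance and take all referrals on those days.
2. State that every patient who meets the non-willingness criteria is approached.
3. Allow diabetes-service referrals to be enrolled, but log them separately, because B1's first denominator names only education referrals.
4. For the first two criteria, define eligibility without inclusion 6, the willingness part of inclusion 4, and exclusion 7. Count unwillingness on any of these as not agreeing. A chart check cannot settle these items.
5. Compute both proportions from the log. Report eligible patients who were not approached separately, with reasons.

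The cost is protocol wording, a log, and chart checks on about 667 referrals if 100 are enrolled at B1's rates, 1,000 at F1's 50% agreement, or 500 if the 100 means patients approached. The fixed-days option eases the daily load. No extra participants are needed. The observed rates may look less favourable.
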